9.5 Identification of Safety Events

As subjects in this study may have pre-existing medical conditions and will be currently hospitalized, those pre-existing conditions will not be considered as adverse events unless they worsen or increase in frequency or intensity after administration of study drug. New events that occur or the worsening in frequency or intensity of pre-existing conditions will be reported as adverse events or, if serious reporting criteria are met, serious adverse events. Events that do *not* qualify as a study drug-related serious adverse event for the STRESS trial and should not be recorded in the IBM Clinical Development clinical database are:

- Medical or surgical procedures (e.g. surgery, transfusion); however, the condition that required the procedure is considered an adverse event if the situation developed or worsened due to study drug administration
- Pre-existing diseases or baseline conditions present or detected before the start of study drug that do not worsen in frequency or intensity due to study drug administration.
- Any events considered to be related to the patients underlying heart disease or recovery from his/her cardiac surgery, including any of the post-operative complications listed in the STS-CHSD.
- Serious Adverse Events that are assessed by the site investigator as Not related or Unlikely related to study drug

9.6 Safety Monitoring

The data coordinating center (DCC) will monitor safety during the conduct of the study. The study sponsor will review all potential unexpected study drug related serious adverse events at the time of SAE notification by DCRI Safety Surveillance and confirm whether the event is a suspected unexpected serious adverse reaction (SUSAR). The data monitoring committee (DMC) will monitor safety every 6 months as per the DMC charter. Annual and expedited reports will be submitted to the FDA as required.

9.7 Halting Rules

All patients who receive study medication will be followed for safety. An independent data monitoring committee consisting of three physicians will conduct an internal review of study safety every 6-months of study enrollment. The safety review will include all SAEs and all AEs captured in either the STS-CHSD or the separate IBM Clinical Development clinical database that the data monitoring committee determine are possibly or probably related to the study drug and all patients who discontinued participation in the study early. If >3 subjects experience **active** (not placebo) **study drug-related** SAEs of the same Preferred Term (MedDRA coding), the DMC will be notified. Decisions to halt the trial will be at the discretion of the DMC.

If the study is halted, the AEs will be thoroughly evaluated and study enrollment will not resume until the safety review is completed.

9.8 Reporting Adverse Events to Institutional Review Boards for NIH-Supported Multi-Center Clinical Trials

The site Investigator or designee is responsible for reporting all serious adverse events to the local IRB/REB in accordance with local policies and procedures.

9.9 Follow-up of Subjects after Adverse Events

For Serious AEs with a positive causal relationship to the study drug, follow-up by the investigator is required until the event or its sequelae resolve or stabilize at a level acceptable to the investigator.

9.10 Study Suspension

Study enrollment and administration of study drug/placebo will be stopped for a safety review based upon the recommendations of the DMC.

10 STATISTICS

10.1 Planned Sample Size

The trial's sample size was formulated to provide high power (>90%) for detecting a clinically important treatment benefit in patients randomized to steroids versus placebo as measured by the trial's primary global ranking endpoint categories with testing based on the Wilcoxon rank sum test or, equivalently, the proportional odds logistic regression model score test [24]. The magnitude of the hypothesized treatment effect of steroids versus placebo was quantified by the win difference $P_1 - P_0$ where P_1 is the probability that a randomly selected patient in the steroids group will have a better outcome (higher global ranking category) than a randomly selected patient in the placebo group and P_0 is the probability that a randomly selected patient in the steroids group will have a worse outcome (lower global ranking category) than a randomly selected patient the placebo group. As shown in Table 6, a sample size of approximately 1,200 participants will provide approximately 85% power if the win difference is 0.10 and will provide 95% power if the win difference is 0.12. Thus, the study has good power to detect a meaningful improvement in the probability of a better outcome with steroids compared to placebo. For an alternative perspective on the study's power, the treatment effect of steroids versus placebo may be quantified by specifying the extent to which the odds of having an outcome in one of the k lowest (worst) global ranking categories is reduced in patients randomized to steroids versus placebo, where $k \leq 1$ refers to the odds of death, $k \leq 2$ refers to the odds of death or heart transplant, etc. Specifically, the treatment effect may be quantified by the set of odds ratios

 $OR_{\leq k} = \frac{odds \text{ of having an outcome in category } \leq k \text{ if randomized to steroids}}{odds of having an outcome in category } \leq k \text{ if randomized to placebo}, k = 1,2,...,96,$ where for simplicity we may assume that $OR_1 = OR_2 = \cdots = OR_{96} (\equiv OR)$. As shown in Table 6, a sample size of 1,200 participants will provide approximate 82% power if the odds ratio is 0.75 (i.e. a 25%)

Page 19 of 96

reduction in the odds) and approximately 95% power if the odds ratio is 0.70 (i.e. a 30% reduction in the odds). Thus, the study is well powered under a range of clinically relevant and plausible risk reduction scenarios. For simplicity, power statements above are based on approximate power using a Wilcoxon test ignoring baseline covariates. However, to increase statistical power, analysis of the primary endpoint will be adjusted for baseline covariates, as described in Section 10.3 below. Based on Monte Carlo simulations, a covariate adjusted analysis will increase power by an amount ranging from 3 to 5 percentage points compared to an unadjusted analysis under assumptions consistent with 80%-90% power for the unadjusted analysis.

Table 6. Estimated power as	function of the effect size as quantified by the win difference or odds
ratio assuming $N = 1,200$ (600	per group)

Effect Size Parameter	$\frac{1}{1}$ Win Difference $(P_1 - P_0)$			Odds Ratio (OR)		
Numerical Effect Size	0.10	0.11	0.12	0.75	0.725	0.70
Power (N = 1,200)	85%	91%	94%	82%	90%	95%

Assumptions: Based on two-sided alpha=0.05. Power was calculated as $\Pr[X_{n\Delta}^2 > 3.841]$ where $X_{1,n\Delta}^2$ denotes a chi-squared random variable with 1 degree of freedom and non-centrality parameter $n\Delta$, where n = 1200 and $\Delta = 3(P_1 - P_0)^2/(4\rho)$ (derived from formulas in Zhao et al.[24]) or $\Delta = \log (OR)/(12/\rho)$ (derived from formulas in Whitehead [26]) where ρ is the probability that 3 randomly selected trial participants will not all have outcomes in the same global ranking category. The quantity ρ reflects the reduction in variance due to ties and was set to its maximum possible value $(\rho = 1)$ in order to obtain a conservative lower bound approximation of power for a specified win difference. Calculations do not account for an expected slight loss of power after decreasing alpha to account for interim analyses.

10.2 Statistical Analysis Plan

All major treatment comparisons between the randomized groups will be performed according to the principle of "intention-to-treat"; that is, subjects who received study drug/placebo will be analyzed (and endpoints attributed) according to the group to which subjects were randomized, regardless of subsequent medications or treatment crossover. Statistical comparisons will be performed using 2-sided significance tests.

10.3 Analysis of the Primary Endpoint

The trial's global ranking endpoint outcome is an ordinal categorical variable having K levels, where category 1 represents the worst possible outcome (e.g. death) and category K represents the best possible outcome (e.g. a short hospital stay free of death or major complications) according to a pre-specified subjective global ranking algorithm (see above). Table 7 summarizes the distribution of ranking endpoints in neonates and infants in a historical cohort of patients from the STS database. The actual observed distribution of ranking categories in the trial will be compared across treatment groups using a stratified non-parametric Wilcoxon rank sum test (also known as the van Elteren test [27]) with stratification by categories of pre-randomization predicted mortality or morbidity risk or by using a regression-based analog of the van Elteren test which allows adjusting for multiple pre-randomization prognostic factors in order to maximize statistical power [28]. Covariates for stratification or covariate adjustment will be determined prospectively and will be pre-specified in the statistical analysis plan. The level of

Page 20 of 96

significance for the assessment of the primary endpoint will be α =0.05 (two-sided). The magnitude of the treatment effect will be described by presenting summary measures of the frequency distribution of ranking categories by treatment group and by estimating the probability that a randomly selected steroids group participant will have a better or worse outcome than a randomly selected placebo group participant (e.g. the win ratio [29]). If the data provide evidence of an overall difference in outcome between treatment groups, we will further examine whether the therapeutic effect is similar for all participants, or whether it varies according to specific participant characteristics, which will be pre-specified in the statistical analysis plan. These analyses will use ordinal regression models and will involve testing for interactions between treatment and these specific baseline variables. Effect estimates for subgroups will be carefully (conservatively) interpreted in conjunction with the formal interaction tests.

Global Rank Endpoints	Age ≤ 30d	Age < 1yr
Operative mortality	8.9%	4.5%
Heart transplant (during hospitalization)	9.2%	5.4%
Renal failure with permanent dialysis, neurologic deficit persistent at discharge, or respiratory failure requiring tracheostomy	10.8%	6.6%
Post-operative mechanical circulatory support or unplanned cardiac reoperation (exclusive of reoperation for bleeding)	19.2%	11.8%
Reoperation for bleeding, delayed sternal closure or post-op unplanned interventional cardiac catheterization	27.1%	16.7%
Post-op cardiac arrest, multi-system organ failure, renal failure with temporary dialysis, or prolonged ventilator support (> 7 days)	36.1%	21.9%
Prolonged post-op length of stay (> 90 days, binary endpoint)	36.6%	22.3%

		-				_
Table 7	Cumulativa	fragmonar	Fondmainte	included in	the global	non z outoomo
Table /.	Cumulative	irequency of	enubornts	menuaea m	the global	ганк онсоше

*Data compiled from the STS Congenital Heart Surgery National Registry (2010-2015)

10.4 Analysis of Secondary Safety and Efficacy Endpoints

Secondary endpoints will be analyzed via regression modeling with adjustment for prerandomization covariates. For secondary endpoints that are binary (e.g. mortality, composite mortality or major complications, low cardiac output syndrome), the form of the model will be a logistic regression comparing the endpoint event rate across the two treatment groups. For continuous outcomes with skewed distributions (e.g., post-operative hospital length of stay, duration of mechanical ventilation) the outcome will be approximated by a skewed distribution such as log-normal, Weibull or negative binomial, or modeled semi-parametrically. For safety analyses, we will summarize the number of adverse events overall, by severity, and by each Medical Dictionary for Regulatory Activities system organ class and preferred term. We will tabulate adverse event data by procedural risk cohort (STAT levels).

10.5 Interim Analyses

Interim examination of clinical endpoints and key safety events will be performed at regular intervals during the course of the trial. An independent Data Monitoring Committee (DMC) will monitor participant safety and review performance of the trial. The primary objective of these interim analyses will be to ensure the safety of the participants enrolled in the trial and evaluate the accumulating endpoint data by treatment group to test for possible differences favoring either Page 21 of 96

of the two randomized management strategies. In addition, interim monitoring will involve a review of participant recruitment, compliance with the study protocol, status of data collection, and other factors which reflect the overall progress and integrity of the study.

Formal interim treatment group comparisons will focus on comparing the distribution of the primary global ranking endpoint categories by treatment group. To account for repeated significance testing of the accumulating data, the group sequential method of Lan and DeMets will be used as a guide for interpreting these interim analyses. Monitoring boundaries for the primary endpoint will be based on a two-sided symmetric O'Brien-Fleming type spending function with an overall two-sided significance level of $\alpha = 0.05$. The O'Brien-Fleming approach requires large critical values early in the study but relaxes (i.e., decreases) the critical value as the trial progresses. These proposed monitoring boundaries are intended as a guide for interpreting the interim analyses and not as a strict rule for early termination. The first interim analysis using alpha spending will be targeted to occur after completion of data collection for the first ~600 to 800 subjects depending on timing of the STS data harvest. Additional interim analyses will be performed at intervals determined by the DMC. Study enrollment will be allowed to continue pending compilation of the interim data and review/recommendations from the DMC.

Update 15 September 2020: Due to a delay in receiving the STS-CHSD data harvest, the DMC Chair is agreeable to proceed with the interim analysis in the following manner. The unblinded statistical team will plan to access and compile Length of Stay (LOS) and mortality data by treatment allocation from the IBM Clinical Development clinical database. This data will be reviewed by the DMC during a convened DMC meeting. If these data suggest any safety concerns, the study team will proceed with the previously planned interim analysis whenever the STS-CHSD data are available. If there are no identified safety concerns then enrollment will continue to trial completion.

10.6 Data Monitoring Committee

A DMC will be appointed by the trial's leadership to monitor participant safety and to review performance of the trial. A DMC charter that outlines the operating guidelines for the committee and the procedures for the interim evaluations of study data will be developed by the trial's leadership and agreed upon by the DMC. Reports will be prepared regularly in accordance with the plan outlined in the charter and as requested by the DMC chair, and will include interim analyses of primary and secondary endpoints; additional safety events; and other information as requested by the committee. After each meeting, the DMC will make recommendations to the trial's leadership about the continuation of the study. After approval by trial leadership, a summary of the DMC report and recommendations will be forwarded to site investigators for submission to their local IRB.

10.7 Population for Analysis

- Efficacy: All participants who receive study drug/placebo.
- Safety: All participants who receive study drug/placebo.
- PK/PD/Biomarkers: All participants who receive methylprednisolone and have at least 1 evaluable PK sample.

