4 TRIAL DESIGN AND METHODS

4.1 Overview

This study is a prospective, double-blind, multi-center, placebo-controlled safety and efficacy study of methylprednisolone in infants undergoing planned heart surgery with CPB. The study will enroll up to 1500 infants (< 1 year of age) including a minimum of 400 neonates \leq 30 days at the time of surgery. The total study duration is expected to be approximately 48 months. An ancillary PK/PD/Biomarker study will enroll subjects at select centers. This study is unique in that it is designed to leverage existing registry infrastructure at participating sites so as to reduce trial costs. Participants will be randomized and will receive a subject ID. This ID will also serve as a unique patient identifier allowing us to crosslink datasets. Participants will then receive study drug/placebo administered into the pump prime during cardiopulmonary bypass. All study participants will then receive routine post-operative care. Participating centers will enter all demographic, preoperative, operative and outcomes data into their existing institutional databases for submission to the STS-CHSD as they currently do. These data will be used to evaluate trial outcomes.

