4.2.2 Blinding

The study medication and the placebo will be identical in appearance to assure masking of study medication. The randomization assignment will be seen only by the statistician at the DCC and the investigational pharmacist preparing the study medication. The family/subject, study coordinator and investigators will remain masked as to treatment group assignment until after all trial data are analyzed.

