4.3.2 Secondary Endpoints (see section 11.2 for data element definitions)

Efficacy:

- Mortality including in-hospital mortality or mortality after hospital discharge but within 30 days of the last dose of study drug
- Death or major complication as defined by an outcome in one of the 6 highest global ranking categories
- Post-operative hospital length of stay
- Prevalence of prolonged (> 7 days) post-operative mechanical ventilation

• Occurrence of post-operative low cardiac output syndrome

Safety:

- Occurence of any one or more of the following STS-CHSD-defined major post-operative infectious complications:
 - Postprocedural infective endocarditis
 - o Pneumonia
 - o Sepsis
 - Deep wound infection
 - Mediastinitis
- Other post-operative complications will be collected from the start of study drug/placebo administration until hospital discharge.

PK/PD/Biomarkers:

- Time to maximum concentration (T_{max})
- Maximum concentration (C_{max})
- Clearance (CL)
- Volume of distribution (Vd)
- Post-operative blood markers of inflammation

PK/PD and Biomarker data will only be collected at select centers and in those patients whose parent/legally authorized representative have granted consent to blood draws. An opt in/out clause is included in the informed consent forms for study participants and centers will be allowed to participate in this part of the study if they prefer. Parent/legally authorized representative of participants may elect to participate in the PK/PD, the Biomarker studies or both. Time points for blood collection will be the same for both the PK/PD and biomarker studies. Biomarkers being collected represent blood markers of inflammation.

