6.5 PK/PD/Biomarker sampling procedures (select sites)

A limited PK/PD/Biomarker sampling scheme will be employed such that no more than 5600 μ l (7 samples, 800 μ l per sample) of blood is obtained (Table 5). Blood samples will be collected in 800 μ L aliquots. Children who have only 1 evaluable PK sample will be included in the analysis, but additional participants may be enrolled to ensure at least 100 children with < 4 adequate PK samples.

Table 5. PK/PD/Biomarker samplin

Sample Number	Per Patient Prioritization	Time	Per patient blood collection
1	Please always try to collect this	Pre-dose (biomarker only)	$4 \ge 200 \text{ uL} = 800 \text{ uL}$
2		0-30 minutes after the start of CPB	
3	Collect a minimum of 2 of any	0-30 minutes after MUF	
4	of these 5 time points to collect	1-2 hours after completion of CPB	4 x 200 uL = 800 uL
5	a minimum total of 3 time	4-6 hours after completion of CPB	$4 \ge 200 \text{ uL} = 800 \text{ uL}$
6	points per participant.	16-24 hours after completion of CPB	
7	If participating in the biomarker arm, then please always try to collect this	36-48 hours after completion of CPB	4x 200 uL = 800 uL

Timed PK/PD/Biomarker sample handling procedures (plasma):

Assays to measure methylprednisolone concentrations and measures of the inflammatory response to CPB in plasma will be conducted at a central lab using validated bioanalytical assays. The date and time will be recorded for the administration of study drug/placebo, and the acquisition time of the PK sample.

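### Section 10.7 gives the inflammatory-marker endpoint the PK population, which contains no placebo infants, so the markers cannot be compared between randomised arms within the stated set

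*Combined protocol and SAP*

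**What the plan says.** Section 10.7 lists three populations. The efficacy and safety rows each take everyone given study drug or placebo. The third row reads "PK/PD/Biomarkers: All participants who receive methylprednisolone and have at least 1 evaluable PK sample".

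Section 4.3.2 lists "Post-operative blood markers of inflammation" as a secondary endpoint, under a PK/PD/Biomarkers subheading together with Tmax, Cmax, clearance and volume of distribution. The same section says that parents "may elect to participate in the PK/PD, the Biomarker studies or both", so a family may join the biomarker part alone.

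Table 5 in Section 6.5 labels sample 1 "Pre-dose (biomarker only") and asks for the 36-48 hour sample from every biomarker participant. Assays of methylprednisolone and "measures of the inflammatory response to CPB in plasma will be conducted at a central lab". Section 6.5 also records administration times for study drug or placebo alongside sample times.

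Section 4.2.2 states: "The family/subject, study coordinator and investigators will remain masked as to treatment group assignment until after all trial data are analyzed". Section 4.1 describes the work as ancillary: "An ancillary PK/PD/Biomarker study will enroll subjects at select centers".

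**The concern.** A rule that is right for PK has been applied to an endpoint of a different kind. Drug concentrations exist only in treated infants, so a treated-only set is natural for PK and for exposure-response. Inflammatory markers exist in both arms, and bypass itself raises them, as the Overview in Section 1 says.

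In a methylprednisolone-only set, two analyses remain. Change over time within the arm mixes the drug effect with the response to bypass and recovery from it. Exposure-response is a non-randomised comparison, in which clearance and exposure may track illness severity. Neither isolates the drug effect as the randomised placebo contrast does.

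The row also requires a PK sample. An infant given methylprednisolone whose family chose the biomarker part only could be dropped for that reason; how many this affects is unknown. Placebo infants would give blood, up to 7 x 800 = 5600 µl each under Section 6.5, for samples that have no place in the defined analysis.

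**Working it through.** The plan gives no biomarker sample size, effect size or SD, so there is no stated figure to reproduce. The check is mainly a comparison of sections, followed by an illustrative calculation.

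**Comparison of sections**

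1. Who is in the set: Section 10.7 requires receipt of methylprednisolone, so placebo n = 0 by definition.
2. Who is sampled: Section 4.2.2 masks families, coordinators and investigators, so sites cannot confine sampling to the active arm. Section 6.5 confirms this by recording times for study drug or placebo.
3. Share left out: allocation is 1:1 (Section 2). Of every 200 infants sampled, about 100 placebo infants fall outside the set, which is half. Some methylprednisolone infants without a PK sample may be lost as well.
4. Any other population: Section 10.2 concerns major comparisons between randomised groups. Section 10.4 is headed safety and efficacy endpoints and describes no biomarker analysis. Neither defines a biomarker set.

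**Illustrative size**

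The only count in the plan is in Section 6.5: "additional participants may be enrolled to ensure at least 100 children". It is a PK minimum, and the sentence goes on to restrict it to children with fewer than four adequate PK samples, an odd qualifier. Using it for biomarkers is an assumption.

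- If the 100 span both arms: about 50 methylprednisolone and 50 placebo.
- If the 100 are all methylprednisolone infants: about 100 placebo infants are sampled as well.

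Detectable difference in SD units, 80% power, two-sided 0.05, n per arm, with correlation r between pre-dose and post-operative values:

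d = (1.960 + 0.842) x sqrt(2/n) x sqrt(1 - r²)

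| n per arm | r = 0 | r = 0.5 (assumed) |
|---|---|---|
| 50 | 2.802 x 0.2000 = 0.560 | 0.560 x 0.866 = 0.485 |
| 100 | 2.802 x 0.1414 = 0.396 | 0.396 x 0.866 = 0.343 |

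The noncentral t at r = 0 gives 0.566 and 0.398, in agreement. Over a wider assumed range at r = 0, the figure runs from 2.802 x sqrt(2/25) = 0.79 SD at 25 per arm to 2.802 x sqrt(2/300) = 0.23 SD at 300 per arm.

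In the set as written the placebo arm has n = 0, so the contrast cannot be estimated at any sample size.

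**The case against.** The strongest objection is that no stated analysis is broken. The plan never says that markers will be compared between arms. The endpoint sits apart from the efficacy and safety lists, and the synopsis gives single-dose PK/PD as the purpose of the blood sampling. A treated-only exposure-response analysis would fit that purpose. This is true as far as it goes: the point is that the rule excludes the more informative analysis, not that a promise is contradicted.

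Sections 10.2 and 10.4 could be read as bringing the markers into a two-arm analysis, since the endpoint is formally secondary. Section 10.2 is limited to major comparisons and Section 10.4 to safety and efficacy, while Section 10.7 names biomarkers explicitly. At best the sections are ambiguous, and that also calls for a correction.

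Section 10.3 refers to a statistical analysis plan for further detail, and a different biomarker set there cannot be excluded. Section 10.3 defers only covariates and subgroup characteristics to it, not populations. If such a set exists, Section 10.7 conflicts with it and still needs aligning.

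The SD figures are only illustrative, because they rest on a PK count and an assumed correlation. That stands. So does the point that PK sample may be loose wording for any post-dose sample, which would shrink the second exclusion. Neither affects the absence of placebo infants.

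**Conclusion.** The concern holds. Followed literally, Section 10.7 leaves no placebo infants in the biomarker analysis, although the design samples them and they are about half of those sampled under 1:1 allocation. This follows from the wording and rests on no assumed number.

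The size in infants and SD units is conditional. If biomarker sampling is similar in number to the PK target and allocation is 1:1, about 50 to 100 placebo infants are excluded. The comparison given up could detect 0.56 to 0.40 SD, or 0.49 to 0.34 SD if the pre-dose correlation is 0.5.

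The consequence is limited to an ancillary, optional part of the trial, and the primary endpoint and the listed efficacy and safety endpoints are not touched. It should be fixed because the repair is nearly free and because choosing the comparison set after unblinding would be open to challenge.

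**What to change.** Split the row in Section 10.7:

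- PK and PK/PD (exposure-response): keep the present rule.
- Biomarkers: all participants who receive study drug or placebo and have at least one evaluable post-operative biomarker sample, analysed as randomised.

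That is the minimum change. It is also worth stating the analysis. A suitable choice is a longitudinal model of the marker, logged if skewed, over the Table 5 windows, with the pre-dose value included as a response and given a common mean in both arms. This adjusts for pre-dose level, keeps infants whose pre-dose sample is missing, and allows for families giving different subsets of samples 2 to 6. Report the arm difference at each window, including 36-48 hours. Name the markers before unblinding.

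The cost is wording in the protocol and analysis plan. Sampling and consent are already planned in both arms, so no new samples or sites are needed.
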